# 4. PLANNED ANALYSES

The following analyses will be performed for this study:

Final Analysis

## 4.1. Interim Analysis

There is no planned or unplanned interim analysis for this study.

# 4.2. Final Analysis

All final, planned analyses identified in this SAP will be performed by IQVIA Biostatistics following Sponsor (Arena Pharmaceuticals, Inc., a wholly owned subsidiary of Pfizer Inc., hereafter referred to as Arena) authorization of the SAP, database lock, analysis sets, and unblinding of treatment. After Arena has authorized breaking of the study blind, the final analysis will be performed.

Any, post hoc, exploratory analyses completed to support planned study analyses, which were not identified in this

Document: \quintiles.net\enterprise\Apps\sasdata\SASb\SAS\Arena\APD334\RZA28116\Biostatistics\Documenta

tion\SAP\503-Final SAP v2.0\APD334-203 SAP Final v2.0-20231120 clean.docx

Author: PPD Version Number: 2.0

Version Date: 20Nov2023

Template No.: CS\_TP\_BS016 Revision 7 Reference: CS\_WI\_BS005

Effective Date: 01Nov2021

PROTOCOL APD334-203

Statistical Analysis Plan

Page 19 of 70

SAP, will be documented and reported in the clinical study report (CSR). Any results from these unplanned analyses will also be clearly identified in the text of the CSR (ICH, 1995).

# 5. ANALYSIS SETS

Agreement and authorization of participants included/excluded from each analysis set will be conducted prior to the unblinding of the study.

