6.5. Blinding

This is a double-blind study with limited access to the randomization code. The study treatment and placebo tablets and bottles are identical in physical appearance. The treatment each participant receives will not be disclosed to the Investigator, study site staff, participants, sponsor personnel involved with the conduct of the study (with the exception of the clinical supply staff and designated safety staff), or study vendors. The IWRS will hold treatment codes and bottle numbers for study treatment.

Treatment assignments should remain blinded unless that knowledge is necessary to determine participant emergency medical care. In case of an emergency, the Investigator has the sole responsibility for determining if unblinding of a participant's treatment assignment is warranted to provide appropriate medical care. Participant safety must always be the first consideration in making such a determination. The IWRS is programmed with blind-breaking instructions to guide the Investigator on how to obtain treatment assignment in the event of an emergency unblinding. The Investigator is requested to contact the Medical Monitor promptly in case of any treatment

unblinding. If a participant's treatment assignment is unblinded, the Sponsor must be notified within 24 hours after breaking the blind. The date and reason the blind was broken must be recorded in the source documentation and eCRF, as applicable.

For Suspected, Unexpected, Serious Adverse Reactions, the Sponsor's Pharmacovigilance designee responsible for managing SAEs will access the IWRS to obtain the participant's treatment assignment for the purpose of regulatory reporting.

If a participant's treatment assignment is unblinded for any reason, they will be discontinued from the study.

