9.7. Pharmacokinetics

Blood samples for analysis of etrasimod will be collected at the following timepoints from all participants who received at least 1 dose of study drug (etrasimod or placebo):

- Predose and at 4 hours (\pm 15 minutes) postdose (after 12-lead ECG) on Week 0/Day 1
- Predose (trough; within 60 minutes prior to dosing) at Weeks 2, 4, 8, and 12, for participants enrolling in the OLE at the Week 12 visit, the PK sample can be collected as part of the OLE.
- At 2-Week and 4-Week Follow-Up visits
- If possible, at the time of any SAE or adverse event leading to study treatment discontinuation

Participants should be instructed to document the time of their last dose prior to the study visit and the time must be recorded in the eCRF. The time of administration of study treatment during the study visit must also be recorded in the source along with the time of each PK sample.

Blood samples will be processed for collection of plasma fractions for determination of the concentrations of etrasimod. For the placebo group, a selected number of samples will be analyzed.

Plasma PK samples may also be used for profiling of drug-binding proteins, bioanalytical method validation purposes, stability assessments, or to assess other actions of etrasimod with plasma constituents.

No urine samples will be collected for PK analysis.

Sample collection, preparation, and shipping will be detailed in a Laboratory Manual.

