## 5.4. Per Protocol Set (PPS)

The Per Protocol Set will consist of all participants in the FAS who adhere to the protocol. This set will be used in supplementary analyses of the primary endpoints to evaluate the influence of major protocol violators and protocol deviators on the primary results.

Participants may be excluded from the PPS if they violate the eligibility criteria or significantly deviate from the study plan, including, but not limited to:

Overall study treatment noncompliance (< 80 or > 120%)

Document: \quintiles.net\enterprise\Apps\sasdata\SASb\SAS\Arena\APD334\RZA28116\Biostatistics\Documenta

tion\SAP\503-Final SAP v2.0\APD334-203\_SAP\_Final v2.0-20231120\_clean.docx

Author: PPD Version Number: 2.0

Version Date: 20Nov2023

Template No.: CS\_TP\_BS016 Revision 7 Reference: CS\_WI\_BS005

Effective Date: 01Nov2021

Page 20 of 70

- Receive incorrect study treatment for > 7 days
- Use rescue medication (new or dose increase from the highest dose of background treatment for UC received during Screening) or undergo rescue medical procedure that may affect efficacy endpoint at Week 12
- Miss Week 12 endoscopic score (ES) in prespecified analysis window (per Section 6.4) for reasons other than
   UC flare or discontinued due to disease worsening or lack of efficacy

Refer to APPENDIX 5 for the definition of rescue therapies (medication and medical procedures). All protocol deviations will be reviewed in addition to the programmable deviations (eg, study treatment noncompliance) to determine if any deviation is significant enough to exclude a subject from the Per Protocol Set. All exclusion flags will be finalized before study unblinding. Participants excluded from Per Protocol Set will be listed along with the reason category above. Participants will be summarized by treatment to which they were randomized, regardless of treatment actually received.

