# 5.7. Pharmacokinetic Set (PKS)

The Pharmacokinetic Set will include all subjects in the Safety Set with at least 1 quantifiable postdose PK measurement of etrasimod which is not impacted by protocol violations or events with potential to affect the PK concentration

Document: \quintiles.net\enterprise\Apps\sasdata\SASb\SAS\Arena\APD334\RZA28116\Biostatistics\Documenta

tion\SAP\503-Final SAP v2.0\APD334-203\_SAP\_Final v2.0-20231120\_clean.docx

Author: PPD Version Number: 2.0

Version Date: 20Nov2023

Template No.: CS TP BS016 Revision 7 Reference: CS WI BS005

Effective Date: 01Nov2021

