#### APPENDIX 5. CLASSIFICATION OF RESCUE THERAPY

This appendix outlines the algorithm for the Arena clinical team/medical reviewers to classify rescue therapies for ulcerative colitis (UC) in a blinded manner. This will help establish 1) intercurrent events for the efficacy estimands, and 2) whether a subject will be excluded from the Per Protocol Set(s). All rescue therapies identified by the medical reviewers per the algorithm below will be imported in programming. This process will be repeated until database lock and the list of all rescue therapies identified will be finalized before study unblinding.

Only medications and medical procedures reported on the electronic case report forms (eCRFs) can be assessed whether they are rescue therapy for UC. If the exposure happens in the follow-up period (beginning on or after the date of last study treatment administration), then it would not be considered as a rescue therapy.

Biologics with immunomodulatory properties

- Rule:
- Any exposure after first dose
- List of medications
  - Anti-TNFα antibodies:
    - ADALIMUMAB
    - CERTOLIZUMAB
    - CERTOLIZUMAB PEGOL
    - GOLIMUMAB
    - INFLIXIMAB
  - Other Biologics:
    - USTEKINUMAB
    - VEDOLIZUMAB

Non-biologics with immunomodulatory properties

- Immunosuppressants
  - Rules:
    - After first dose and up to and including Week 8: any increase from baseline for more than
       5 days

Document: \quintiles.net\enterprise\Apps\sasdata\SASb\SAS\Arena\APD334\RZA28116\Biostatistics\Documenta

tion\SAP\503-Final SAP v2.0\APD334-203\_SAP\_Final v2.0-20231120\_clean.docx

Author: PPD Version Number: 2.0

Version Date: 20Nov2023

Template No.: CS\_TP\_BS016 Revision 7 Reference: CS\_WI\_BS005

Effective Date: 01Nov2021

Page 67 of 70

- After Week 8: Any dose above baseline
- List of medications
  - MERCAPTOPURINE
  - AZATHIOPRINE
  - TIOGUANINE
  - METHOTREXATE
  - METHOTREXATE SODIUM
- 5-ASA compounds
  - Rules:
    - After first dose and up to and including Week 8: Any increase from baseline for more than 5 days
    - After Week 8: Any dose above baseline
  - List of medications
    - MESALAZINE
    - BALSALAZIDE
    - BALSALAZIDE DISODIUM DIHYDRATE
    - BALSALAZIDE SODIUM
    - OLSALAZINE SODIUM
    - SULFASALAZINE
    - BECLOMETASONE W/MESALAZINE
  - Routes
    - ORAL
    - RECTAL
- Other small molecule immunomodulatory active agents
  - Rules:

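### SAP 5 requires the Pharmacokinetic Set to be authorised before unblinding, but SAP 5.7 defines it by a quantifiable etrasimod level, so authorising it as written reveals active versus placebo

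*SAP*

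**What the plan says.** SAP 5 sets one timing rule for all sets: "Agreement and authorization of participants included/excluded from each analysis set will be conducted prior to the unblinding of the study". No set is exempted there or in the later subsections.

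SAP 5.7 defines the PKS by assay result: "The Pharmacokinetic Set will include all subjects in the Safety Set with at least 1 quantifiable postdose PK measurement of etrasimod", provided that measurement is not compromised by protocol violations or events affecting concentration. Protocol 9.7 adds that "For the placebo group, a selected number of samples will be analyzed".

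SAP 4.2 makes the final analysis follow the sponsor's "authorization of the SAP, database lock, analysis sets, and unblinding of treatment", in that order.

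Two other decisions fall in the same window. For the Per Protocol Set, SAP 5.4 says "All exclusion flags will be finalized before study unblinding". For rescue therapy, SAP Appendix 5 has the sponsor's clinical team and medical reviewers classify blind, repeat the exercise until database lock, and ensure that "the list of all rescue therapies identified will be finalized before study unblinding".

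On the blind itself, Protocol 6.5 says "The treatment each participant receives will not be disclosed to the Investigator, study site staff, participants, sponsor personnel involved with the conduct of the study". Its stated exceptions are clinical supply staff and designated safety staff. Study vendors are also to stay blinded.

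**The concern.** Membership of the Screened, Randomized, Full Analysis, modified Full Analysis, Per Protocol and Safety Sets can be agreed from consent, dosing, visit and deviation records without knowing treatment. The PKS cannot. Barring a dispensing error, only someone who took etrasimod has a quantifiable etrasimod level. To authorise the PKS before unblinding is to see a list that is close to the active-versus-placebo allocation.

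Two judgements need that blind. Per Protocol exclusions include a review of all deviations for whether any is serious enough to remove a participant; this feeds a supplementary analysis of the primary endpoint (SAP 16.1.4). Rescue classification carries more weight, because a rescued participant is a nonresponder in the primary endpoint and the other responder endpoints (SAP 16.1.2, 16.2.2, 16.3.2). Since SAP 3.3 drops all hypothesis tests for efficacy, the estimates and intervals are the efficacy result, and a biased classification would act on them directly.

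**Working it through.** The plan gives no figure on this point. Its one design figure, at least 80% power for 31.5% versus 5% remission with 32 per group (SAP 7), is consistent with recalculation (79.8% with pooled variance, 83.2% with unpooled variance). Nothing below depends on it.

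**Step 1. How much the list reveals.** Inputs: 1:1:1 allocation (SAP 3.1), so two thirds of participants are on etrasimod; 96 planned (SAP 7); PKS rule from SAP 5.7. Let q be the share of etrasimod participants with no usable quantifiable postdose sample. The documents do not give q; 0 to 10% is assumed.

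- Share in the PKS = (2/3)(1 − q)
- Probability that a non-member is on placebo = (1/3) / [1 − (2/3)(1 − q)] = 1/(1 + 2q)
- Share of participants whose class is read correctly = (2/3)(1 − q) + 1/3 = 1 − 2q/3
- A member is on etrasimod, barring dispensing error

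| q (assumed) | Members of 96 | Non-members | Placebo, given non-member | Class read correctly |
|---|---|---|---|---|
| 0% | 64.0 | 32.0 | 100% | 100% |
| 2% | 62.7 | 33.3 | 96% | 98.7% |
| 5% | 60.8 | 35.2 | 91% | 96.7% |
| 10% | 57.6 | 38.4 | 83% | 93.3% |

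The percentages do not depend on the total, so the early stop does not change them. Membership does not separate 1 mg from 2 mg.

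**Step 2. What else is open at that moment.**

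| Decision | Deadline in the SAP | Used in |
|---|---|---|
| PKS membership | before unblinding (SAP 5) | PK summaries |
| Per Protocol flags | before unblinding (SAP 5, 5.4) | supplementary analysis of the primary endpoint |
| Rescue list | repeated to database lock, final before unblinding (Appendix 5) | primary and other responder endpoints |

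Per Protocol flags fall under the same authorisation sentence as the PKS. Rescue review is tied to database lock, which SAP 4.2 lists before the analysis sets, so on that order it would close first. Its binding deadline is still unblinding, and no sentence makes either list final before PKS membership is produced.

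**Step 3. What one changed rescue decision can do.** For a participant who otherwise meets remission, the change in the arm's rate is 1/n. At n = 32, 1/32 = 3.1 percentage points. SAP 7 says the sample will be smaller but gives no number. At an assumed 20 or 12 per arm, the change is 1/20 = 5.0 or 1/12 = 8.3 points. For a participant who does not otherwise meet remission the change is zero, because the outcome is nonresponse either way.

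**The case against.** The strongest reply is that the SAP's own sequence already protects the primary endpoint. SAP 4.2 puts database lock before the analysis sets and Appendix 5 runs rescue review up to lock, so the only decision affecting the primary endpoint should be finished before anyone sees a PKS list. Appendix 5 also leaves limited discretion: it works from named drugs, routes, study periods and day thresholds applied to case report form entries. At the design rates, an average reclassification at 32 per arm would move the estimate by only 0.315 × 3.1 = 1.0 point on 2 mg and 0.05 × 3.1 = 0.16 point on placebo. No test or success decision depends on it, and the PKS feeds no efficacy endpoint.

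Much of this stands, and it rules out several stronger readings that a reader might infer:

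- That rescue decisions will still be open when the PKS is authorised. The documents allow this but do not say it.
- That the same people handle the PKS and the rescue review. The sponsor authorises the sets and its clinical team classifies rescue, but no passage names the individuals.
- That the list reveals dose. It does not, and the documents give no concentrations from which to judge whether the levels would.
- That SAP 19 shows concentrations to the study physician before unblinding. It allows physician input as needed on affected PK data and gives no timing. Its examples (vomiting, sample processing, inaccurate dosing) can mostly be judged without concentrations.
- That no firewall exists. Choosing which placebo samples to assay already requires someone to know allocation, so Protocol 6.5 is evidently not a full list of unblinded roles, and operational documents may cover release of PK data. What can be said is that neither the protocol nor the SAP describes such a safeguard for PK data. For lymphocyte counts, by contrast, Protocol 9.8.4 uses a separate unblinded Medical Monitor.

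The reply does not remove the conflict. SAP 5 covers the PKS by its wording, and the Per Protocol flags are settled at that same step.

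**Conclusion.** The conflict is real and lies in the wording: SAP 5 cannot be applied to the PKS of SAP 5.7 without showing the authoriser active versus placebo, contrary to Protocol 6.5. The disclosure is close to complete, with 93.3% to 100% of participants read correctly if up to 10% of etrasimod participants lack a usable sample.

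The consequence is narrower than the disclosure. The blind may be lost for Per Protocol judgements, which affect only a supplementary analysis, and for rescue classification only if the order implied by SAP 4.2 and Appendix 5 slips. In that event 3.1 points per reclassified participant is the ceiling at 32 per arm, not the expected shift. The ceiling is higher in practice, because the trial stops early and the primary analysis is further restricted to baseline MMS 5 to 9. The risk is bias in the estimates, not type I error, since no efficacy hypothesis is tested.

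This rests on two assumptions: that q is 0 to 10%, and that no operational document not seen here already withholds the PKS list from the blinded reviewers.

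**What to change.** Amend two places in the SAP:

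- **SAP 5:** limit the pre-unblinding authorisation to the Screened, Randomized, Full Analysis (including its MMS 5 to 9 subset), modified Full Analysis, Per Protocol and Safety Sets, and exempt the PKS. SAP 4.2 is then read subject to that exemption.
- **SAP 5.7:** state that sample-level reasons for excluding PK data (dosing, vomiting, sample handling) are fixed before unblinding and without sight of concentrations. State also that PKS membership is derived only after database lock, final rescue and Per Protocol flags, and unblinding.

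The cost is about two sentences, and PKS derivation moves to just after unblinding. Fixing the exclusion reasons beforehand limits the discretion that the later derivation would otherwise allow. No new data or staff are needed, and no sample size or efficacy analysis changes.

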### 5.1. Screened Set

The Screened Set will consist of all participants who sign informed consent to participate in the study.

#### 5.2. Randomized Set

The Randomized Set will consist of all participants who are randomized to study treatment.

For analyses and displays based on Randomized Set, participants will be classified according to randomized treatment.

# 5.3. Full Analysis Set (FAS)

The FAS will consist of all randomized participants who receive at least 1 dose of study treatment. Participants will be summarized by the treatment to which they were randomized, regardless of treatment actually received.

## 5.4. Per Protocol Set (PPS)

The Per Protocol Set will consist of all participants in the FAS who adhere to the protocol. This set will be used in supplementary analyses of the primary endpoints to evaluate the influence of major protocol violators and protocol deviators on the primary results.

Participants may be excluded from the PPS if they violate the eligibility criteria or significantly deviate from the study plan, including, but not limited to:

Overall study treatment noncompliance (< 80 or > 120%)

Document: \quintiles.net\enterprise\Apps\sasdata\SASb\SAS\Arena\APD334\RZA28116\Biostatistics\Documenta

tion\SAP\503-Final SAP v2.0\APD334-203\_SAP\_Final v2.0-20231120\_clean.docx

Author: PPD Version Number: 2.0

Version Date: 20Nov2023

Template No.: CS\_TP\_BS016 Revision 7 Reference: CS\_WI\_BS005

Effective Date: 01Nov2021

Page 20 of 70

- Receive incorrect study treatment for > 7 days
- Use rescue medication (new or dose increase from the highest dose of background treatment for UC received during Screening) or undergo rescue medical procedure that may affect efficacy endpoint at Week 12
- Miss Week 12 endoscopic score (ES) in prespecified analysis window (per Section 6.4) for reasons other than
   UC flare or discontinued due to disease worsening or lack of efficacy

Refer to APPENDIX 5 for the definition of rescue therapies (medication and medical procedures). All protocol deviations will be reviewed in addition to the programmable deviations (eg, study treatment noncompliance) to determine if any deviation is significant enough to exclude a subject from the Per Protocol Set. All exclusion flags will be finalized before study unblinding. Participants excluded from Per Protocol Set will be listed along with the reason category above. Participants will be summarized by treatment to which they were randomized, regardless of treatment actually received.

# 5.5. Modified Full Analysis Set (mFAS)

The mFAS will consist of all randomized participants who receive at least 1 dose of study treatment and have a Baseline and at least 1 post-randomization measurement. Participants will be summarized by treatment to which they were randomized, regardless of treatment actually received. Note that the mFAS can vary with endpoints since some participants may have the needed data for inclusion in the mFAS for some endpoints but others may not.

# 5.6. Safety Set (SS)

The safety set (SS) will include all randomized participants who receive at least 1 dose of study treatment.

Participants will be analyzed according to the treatment received, regardless of randomization. The Safety Set will be used for all safety analyses.

# 5.7. Pharmacokinetic Set (PKS)

The Pharmacokinetic Set will include all subjects in the Safety Set with at least 1 quantifiable postdose PK measurement of etrasimod which is not impacted by protocol violations or events with potential to affect the PK concentration

Document: \quintiles.net\enterprise\Apps\sasdata\SASb\SAS\Arena\APD334\RZA28116\Biostatistics\Documenta

tion\SAP\503-Final SAP v2.0\APD334-203\_SAP\_Final v2.0-20231120\_clean.docx

Author: PPD Version Number: 2.0

Version Date: 20Nov2023

Template No.: CS TP BS016 Revision 7 Reference: CS WI BS005

Effective Date: 01Nov2021

# 6. GENERAL CONSIDERATIONS

# 6.1. Reference Start Date and Study Day

Study Day will be calculated from the reference start date and will be used to show start/stop day of assessments and events. It will appear in listing where an assessment date or event date appears.

Reference start date is defined as the day of the first dose of study medication (Day 1 is the day of the first dose of study medication).

If the date of the event is on or after the reference date, then:

Study Day = (date of event - reference start date) + 1

If the date of the event is prior to the reference date, then:

Study Day = (date of event - reference start date)

In the situation where the event date is partial or missing, Study Day, and any corresponding durations will appear partial or missing in the listings.

### 6.2. Baseline

Unless otherwise specified, baseline is defined as the last non-missing measurement taken prior to the first dose administration (including unscheduled assessments). If measurements include time (except for health-related quality of life [HRQoL] instruments), the date/time will be used to define Baseline. Otherwise, only dates will be compared. For HRQoL instruments, only the date will be used to derive Baseline. In the case where the last non-missing measurement and the date of first dose administration coincide and time is not collected, if the measurement was planned in the protocol to be done prior to the date of first dose, that measurement will be considered in defining Baseline.

